## Safety Analyses

All-cause mortality will be quantified by the count of deaths per person-months (28 days) of observation by intervention/usual care group. These values will be computed overall and stratified by study phase. Thus, the maximum follow-up period for mortality (and other safety outcomes) is 90 days after SNF discharge. Cox proportional hazards regression will be used to quantify statistical uncertainty about the effect of intervention on

the hazard of death (overall and separately within study phase), which will be summarized using the hazard ratio and corresponding Wald-type 95% confidence interval.

The incidence and timing of (potentially recurrent) adverse events will be quantified, for each type of event both overall and stratified by study phase, by counting the number and fraction of affected participants, by tabulating the number of events per participant, and the total number of events per person-months. The effect of the intervention on the hazard of each adverse event type (overall and separately within study phase) will be quantified using Cox proportional hazards regression in a recurrent events (frailty) configuration, which accounts for between-subject heterogeneity in the baseline hazard of recurrent events. In other words, this approach accounts for the within-subject correlation among recurrent event times. The hazard ratio will be summarized using a Wald-type 95% confidence interval.

If there are sufficiently many events, the Nelson-Aalen estimator of the baseline hazard will be used in conjunction with the estimated hazard ratio to estimate median survival with Wald-type 95% confidence interval, for each type of adverse event. Graphical regression diagnostics will be used to evaluate model fit and modeling assumptions of the Cox proportional hazards method.

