## Schedule of Assessments

**Table 1. Data Collection Schedule**

Measures	Baseline Hospital	SNF*	Post SNF Discharge		
			7-Days Telephone Person	60-Days Telephone	90-Days In- Person
Descriptives					
Demographics and Length of Stay	X	X			
Charlson Comorbidity Index	X				
Adverse Drug Event Risk Score	X				
Walter Index (Life Expectancy)	X				
Patient Attitudes Toward Deprescribing (PATD)	X				
Primary Outcome – Medications					
Total number of Routine & PRN Medications	X	X	X	X	X
Total number of potentially inappropriate medications (PIMs) and medications associated with geriatric syndromes (MAGS)	X	X	X	X	X
Drug Burden Index (DBI)	X	X	X	X	X
Secondary Outcomes – Geriatric Syndromes, Adherence, Functional Health					
Cognitive Impairment (BIMS)	X	X	X		X

Delirium (BCAM)	X	X			X
Depression (PHQ-9)	X	X	X		X
Urinary Incontinence (ICIQ-UI SF)	X	X	X		X
Unintentional Weight Loss (DETERMINE)	X	X	X		X
Pain (Brief Pain Inventory, BPI-short form)	X	X	X		X
Falls	X	X	X	X	X
Pressure Ulcers	X	X			X
Medication Behavior (ARMS)	X			X	X
Functional Health Status (VES-13)	X		X		X

*Safety and Healthcare Utilization Outcomes*

Unplanned Healthcare Utilization (Hospitalizations, emergency room visits)		X	X	X	X
Adverse Drug Withdrawal Events & Adverse Drug Events	X	X	X	X	X
Status: Long-Term Care, Hospice, Death		X	X	X	X

\*Secondary outcome measures at SNF phase were assessed by SNF personnel as part of their routine MDS assessments

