**Descriptions of Assessments**

Demographic and Administrative Data: The sociodemographic data collected during this investigation is obtained from multiple sources, including subjects (or proxies) directly via standardized interview protocols and medical records review. Utilizing a standardized form to abstract information from the electronic medical record, a member of the project team collects age, gender, race/ethnicity, home address/telephone contact information, insurance status, outpatient providers and pharmacies, brief health literacy score, and highest education level. We also abstract from the site immediately prior to hospital admission, hospital admission and discharge dates (length of stay), admission diagnoses, hospital service/team, and discharge destination (SNF name/location). Social security number is abstracted and recorded to process the participant payment. These data are verified with the patient or surrogate during the bedside baseline interview. We also track SNF discharge date and length of stay.

Charlson Comorbidity Score ranges from 0 to 31, with a higher score indicating more comorbid illness. There is an additional one-unit increase in the weighted score for every decade starting from age 50. Data sources for comorbidities are the ICD-9 and ICD-10 diagnostic criteria from the 12 months prior to hospital discharge found on the patient’s Problem List in the EMR.

GerontoNet Adverse Drug Event risk assessment calculates the older patient’s risk for an adverse drug event. The components of the risk assessment include certain medical diagnoses or comorbidities (e.g., chronic kidney disease), which are assessed through ICD-10 codes, notations on patient’s problem list, and patient’s medical history on their hospital intake and assessment form. The other component is a previous adverse drug reaction, which is included in the bedside baseline interview.

Walter Index is a prognostic tool to predict one-year mortality among older adults after hospital discharge with a higher score indicating a greater likelihood of mortality. The comorbidities and lab values are abstracted from the medical record review, and the activities of daily living assistance is completed based on both medical record review and patient interview.

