### Interim analyses and Stopping Rules

Interim analyses will be conducted to evaluate safety endpoints but will not be conducted to evaluate conditional power (futility) or to assess efficacy.

Safety is evaluated by examining group differences in death and serious adverse events semi-annually in conjunction with scheduled DSMB meetings to evaluate the safety of the study intervention, and the associated risk-to-potential benefit ratio. The Principal Investigators will address study efficacy only at the end-of-study, and thus will not consider terminating the trial early on the basis of conditional power (futility) or evidence of efficacy. This is because firm evidence will be required to change current clinical practice, and because trials that have stopped early for efficacy often report implausibly large effect sizes (and therefore should be considered with skepticism). At the conclusion of each DSMB meeting, the Board should take into account the statistical evidence (as summarized by the relative hazard of safety endpoints and the corresponding 95% confidence interval) as well as practical and clinical considerations to make one of the following recommendations based on safety:

1. Suspend enrollment due to safety concerns secondary to study intervention including:

- a. A difference in all-cause mortality between patients randomized to the deprescribing intervention versus usual care such that the DSMB deems the difference to be study-related and excessive.
  - b. A difference in drug related SAEs between patients randomized to the deprescribing intervention versus usual care such that the DSMB deems the difference to be study-related and excessive.
2. Continue enrollment

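### The mortality Cox model names no baseline covariate although the Walter Index is collected, so chance imbalance in prognosis stays uncorrected in the hazard ratio the DSMB weighs

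*Combined protocol and SAP*

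**What the plan says.** Under Statistical Considerations, Safety Analyses, mortality is summarised as deaths per person-month by arm. Then "Cox proportional hazards regression will be used to quantify statistical uncertainty about the effect of intervention on" the hazard of death, overall and within study phase, with a Wald 95% interval. No baseline covariate is named there or in any other section. Recurrent adverse events get a Cox model with a frailty term that "accounts for between-subject heterogeneity in the baseline hazard of recurrent events".

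Under Interim Analyses and Stopping Rules, the DSMB considers the statistical evidence, "as summarized by the relative hazard of safety endpoints and the corresponding 95% confidence interval", together with practical and clinical considerations. No alpha, boundary, target hazard ratio or power for harm is set.

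Descriptions of Assessments states that the "Walter Index is a prognostic tool to predict one-year mortality among older adults after hospital discharge". It describes the GerontoNet score as an assessment of the older patient's "risk for an adverse drug event". Table 1 lists both under descriptives, in the baseline hospital column only. Data Analyses uses baseline factors only to summarise balance between the arms, and states that there is no stratification. By contrast, the medication-count model (Outcomes, Hypotheses 1a-1b) does adjust for a baseline value, the enrollment medication count.

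**The concern.** A score built to predict death after hospital discharge is recorded at baseline and then plays no part in the comparison of deaths. With no stratification by risk, one arm can be healthier by chance. The DSMB could see this in a baseline table but would have no pre-specified way to allow for it, and a covariate chosen after an imbalance is seen carries little weight. In a Cox model, omitting a prognostic covariate also moves the estimated hazard ratio towards 1 relative to the covariate-adjusted one, which lowers power somewhat. The mortality hazard ratio is part of the evidence for suspending enrollment. With no numerical boundary, the estimate and its interval must carry the statistical side of that judgement.

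**Working it through.** **Inputs from the documents.** Enrollment is 144 x 4 = 576, allocated 1:1. Attrition from death and loss together is 27.5%, and 576 x (1 - 0.275) = 417.6 agrees with the stated 420. Safety follow-up ends 90 days after SNF discharge and the mean post-acute stay is 26.9 days, so follow-up is about 90 + 26.9 = 117 days from hospital discharge. The plan states no safety power to reproduce.

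**Assumptions.** The death proportion, the true hazard ratio and the strength of the score are not given, so ranges are used.

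**Step 1: power from deaths alone, unadjusted, two-sided 5%.** Power = Phi(ln(HR) x sqrt(D)/2 - 1.96), where D is the number of deaths.
- With 10% deaths, D = 58. At HR 1.5: 0.405 x 7.62/2 - 1.96 = -0.42, so power is 34%.
- With 20% deaths, D = 115 and power is 59%.
- Deaths needed for 80% power = 4 x (1.96 + 0.84)^2 / ln(HR)^2, which gives 191 at HR 1.5 and 66 at HR 2.0.

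**Step 2: gain from adjustment.** Simulated Cox models, N = 576, 2,000 runs per setting, with and without one normally distributed score. Score effects of 0.5, 0.75 and 1.0 log-hazard per SD correspond to a C-index of about 0.64, 0.70 and 0.75. Power is shown as unadjusted to adjusted:

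| Control deaths | HR | 0.5 per SD | 0.75 per SD | 1.0 per SD |
|---|---|---|---|---|
| 5% | 1.5 | not shown | 19.7 to 19.7% | 18.4 to 19.3% |
| 10% | 1.5 | 36.1 to 37.0% | 34.6 to 37.7% | 32.4 to 37.0% |
| 20% | 1.5 | 62.7 to 65.8% | 61.3 to 68.2% | 53.5 to 64.5% |
| 27.5% | 1.5 | 74.6 to 79.2% | 68.6 to 78.6% | 62.1 to 78.5% |
| 5% | 2.0 | not shown | 56.5 to 59.1% | 52.6 to 57.3% |
| 10% | 2.0 | 85.4 to 87.2% | 83.2 to 86.3% | 78.4 to 85.6% |

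At 5 to 10% control deaths the gain is 0 to 7 points. Gains of 10 to 16 points appear only in the 20% and 27.5% rows, with effects of 0.75 to 1.0 per SD. With no true effect, both models reject in about 4 to 6% of runs. The standard error does not fall (0.244 unadjusted, 0.245 adjusted at 10% deaths, HR 1.5, 0.75 per SD). The gain comes from the estimate, 1.48 unadjusted against 1.50 adjusted in that setting.

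The percentages are control-arm deaths, as the standard errors confirm. At 27.5% and HR 1.5, 4/0.149^2 = 180 deaths, or 31% of 576. At 20%, 4/0.174^2 = 132 deaths, or 23%.

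**Step 3: chance imbalance.** For a standardised score, the difference in arm means has SD 2/sqrt(N). Assume 0.7 log-hazard per SD.
- N = 144: SD = 0.167, and exp(+/-1.96 x 0.167 x 0.7) gives a factor of 0.80 to 1.26 on the hazard ratio.
- N = 576: SD = 0.083, giving a factor of 0.89 to 1.12.

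A separate simulation used true HR 1.6 and 1,000 runs. In the fifth of trials where the intervention arm was healthier by chance, unadjusted power was 36% (adjusted 47%) at 10% control deaths and 49.5% (adjusted 69%) at 15%. The unadjusted HR averaged 1.44 to 1.47, the adjusted 1.58 to 1.63. Each such fifth holds 200 trials, so these powers carry a Monte Carlo standard error of up to sqrt(0.25/200) = 3.5 points.

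**The case against.** The case against giving this much weight is substantial, and most of it stands.

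- **The gain may be near zero.** At HR 1.6 with a weaker score (0.4 per SD), power was 27.5 to 27.2%, 50.5 to 51.1%, 67.2 to 68.7% and 77.0 to 79.4% at 5, 10, 15 and 20% control deaths. The score may also discriminate less well here. Follow-up is about 117 days rather than a year, enrollment starts at age 50, patients expected to live under 6 months are excluded, and those moved to hospice are withdrawn.
- **The largest gains strain the plan's own attrition figure.** The 31% deaths behind the 16-point gain exceed the 27.5% allowed for deaths and losses together, and 23% leaves little room for loss. The simulations also follow all 576 patients fully, whereas the analyses are limited to those discharged to a partner facility.
- **The number of deaths matters far more.** Going from 58 to 115 deaths adds 25 points at HR 1.5 (34 to 59%).
- **Early looks are too sparse.** Half a year of enrollment is 72 patients. At an assumed 10% mortality that is about 7 deaths, too few to make an adjusted model dependable.

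A reader might also infer four stronger points that the documents do not support. First, that the unadjusted hazard ratio is biased: it is a valid marginal quantity, and its interval allows for chance imbalance on average, though not given the imbalance actually seen. Second, that the plan gives away power for harm: it sets none. Third, that both scores were collected for exactly these outcomes: they are listed as descriptives, the Walter Index has a one-year horizon, and an adverse event here is any unplanned utilization or unexpected death. Fourth, that the adverse-event models fail in the same way. The frailty term already absorbs part of the patient-to-patient variation, and a recurrent-event simulation at HR 1.3 found a gain of only 0.4 to 6 points. In addition, the outpatient study described under Physiologic Drug Withdrawal found no association of baseline comorbidities with withdrawal events.

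**Conclusion.** The point holds for the mortality model. It names no covariate, a relevant score is already collected, allocation is not stratified by risk, and the resulting hazard ratio is part of the DSMB's evidence. The firmer benefit is a pre-specified way to allow for an observed imbalance in prognosis, which protects against a false alarm as well as a missed signal. The average power gain is modest: 0 to 7 points at 5 to 10% control deaths, and 10 to 16 points only with many deaths and a fairly strong score. These figures depend on assumed death rates, hazard ratios and score effects. The omission does not invalidate the safety analysis; this is a low-cost improvement worth making. For the adverse-event models there is no comparable case.

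**What to change.** In Safety Analyses, add a hazard ratio for death adjusted for the baseline Walter Index as a continuous covariate, reported beside the unadjusted one at the final analysis. State how missing components of the index are handled, for example by imputation from baseline data only, without reference to arm or outcome.

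In Interim Analyses and Stopping Rules, say that DSMB reports will show both hazard ratios once deaths reach a minimum fixed in advance, and that earlier looks rely on the unadjusted one. Adjusting drug-related event models for the GerontoNet score is optional and should be labelled supportive.

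The cost is a few sentences, a little imputation and one more model, with no new data. The adjusted hazard ratio is conditional on the score and the unadjusted one is marginal. The two need not agree even without imbalance, so the text should say which is which.

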## **STUDY DESIGN**

The study is a 5-year, randomized controlled clinical intervention trial at a singular academic medical center.

Primary Outcomes are change in total number of medications including the number of potentially inappropriate medications, number of medications associated with geriatric syndromes, and medications that contribute to anticholinergic and sedative drug burden.

Secondary Outcome is the impact of deprescribing on prevalence and severity of geriatric syndromes, medication adherence, and functional health status.

Eligible patient population is aged 50 years or older, experiencing polypharmacy as defined by 5 or more home medications, and hospitalized at VUMC with a referral to partner post-acute care facility.

Exclusion criteria include limited life expectancy (less than 6 months), non-English speaking, no telephone, homeless or incarcerated, enrolled in another drug trial, and expected to discharge from VUMC in less than 48 hours.

The primary study setting is Vanderbilt University Medical Center (VUMC), a private, non-profit, tertiary care teaching organization located in Nashville, Tennessee. The medical center is a principal referral center for physicians and patients throughout the Southeast, and it serves a diverse population in terms of income, geography, and education level. We will work with patients discharged to 20 SNFs and 2 IPRs within a nine-county radius of Nashville. The target PACs are all for-profit and comparable to PACs in the middle TN area based on publicly reported staffing and quality indicators ([www.medicare.gov](http://www.medicare.gov)).

The timeline for the study is 5 years with enrollment beginning in March 2017 and enrollment closing at the end of October 2020.

The Shed-MEDS intervention is a multistep deprescribing protocol which considers patient and disease factors, life expectancy, goals of care, and appropriate treatment targets. Medication-specific factors such as drug-drug interactions, drug-disease interactions, and drug-specific safety profiles are also incorporated. Finally, patient preferences and primary prescriber input are key to final deprescribing actions by identifying the medications patients are willing to discontinue and seeking their primary prescriber's agreement. In this intervention, deprescribing is defined as either stopping a medication or reducing the dose/frequency of a medication.

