## PAC Handover and Ongoing Deprescribing at PAC Facility

Within 24-hours of transition to PAC, a study pharmacist or NP has a phone conversation with a designated PAC provider with prescribing authority (NP or physician) to review the Transfer Medication List, highlight deprescribed medications and the need for medication-specific monitoring. In addition, all medications recommended for deprescribing may not be stopped prior to hospital discharge in the interest of first monitoring symptoms and ensuring safety or due to delayed contact and input from the outpatient prescriber. Medications for additional deprescribing at the PAC may be highlighted during this initial handover and discussed again in weekly follow-up calls while the patient remains in PAC (Phase 3).

Following PAC handover, we initiate a weekly conversation via telephone with the designated PAC provider to review intervention participants' medication administration record (MAR) and any drug withdrawal events. Reasons for modifying the Transfer Medication List during the PAC stay will be discussed and intervened upon as necessary. The intervention also will continue for participants readmitted to VUMC directly from PAC (estimated 20%) and continue upon transfer back to the PAC. The study PharmD or NP may also continue to communicate with the original prescriber/ outpatient provider during the PAC stay to confirm their agreement with medication changes. At the time of discharge from the PAC facility, a final reconciled medication list will be sent to the patient's primary outpatient providers along with suggestions for continued medication management and deprescribing as well as any explanations for other medication changes made.

For analytical and feasibility purposes, the intervention ends at the point of discharge to home. If a patient discharges to home instead of a partner PAC facility, they will be withdrawn from the study and only considered to have one phase of the intervention. For safety reasons, the study team provides their outpatient provider with the final discharge medication list highlighting any symptom monitoring required.

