## Approach to potential risks of the proposed study

The potential risks of deprescribing medications include, but are not limited to, adverse drug withdrawal reactions, pharmacokinetic and pharmacodynamic changes in other medications, and return of a medical condition.

Physiologic Drug Withdrawal: In retrospective studies of medication cessation, 1 in 5 older outpatients experienced an adverse withdrawal reaction, however only 12% of these reactions were assessed to be physiological reactions to medication withdrawal. These included B-blockers, benzodiazepines, clonidine, nortriptyline, and prednisone. The only risk factor for ADWE found in this study was the number of medications stopped (OR = 1.90, 95% CI 1.33 to 2.67). All reactions occurred within 30 days of discontinuation. Patient age, baseline comorbidities, and number of baseline medications were not associated with ADWEs. A separate study showed that only 1% of unplanned emergency department visits were due to withdrawal reactions. We will mitigate the potential for physiologic withdrawal by identifying those medications with the highest likelihood of physiological withdrawal, including benzodiazepines, opiates, B-blockers, alpha blockers, and tricyclic antidepressants. Any medication believed to have increased potential for physiologic withdrawal will undergo a prescribed drug taper, where the identified drug will not be reduced by more than 25% during any 1 week interval when a patient is receiving greater than the minimum therapeutic dose. In addition to staged tapering of the medication, patients will be receiving continued care in a post-acute care facility, where patients are observed daily by licensed nurses for vital sign and symptom changes. Medications can be restarted or increased at any time should a physiologic drug withdrawal effect be detected.

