Pharmacokinetic and Pharmacodynamic Changes: Medication cessation may additionally alter pharmacokinetic and pharmacodynamic profile of medications. This may include medications that inhibit or potentiate the cytochrome P450 enzyme inhibitor, thus altering clearance of specific medications. Alternatively, some medications may have opposing effects on blood pressure or electrolytes (e.g., potassium). All deprescribing actions will be made by a trained pharmacist and clinicians. In the case that there is believed to be a potential change in pharmacokinetics or pharmacodynamics, deprescribing pharmacists / NPs will alert the primary medical team and make recommendations for surveillance of symptoms, signs (e.g., vital signs), labs (e.g., electrolytes, INR), or follow-up tests (e.g., EKG). Medications can be restarted or increased at any time should adverse pharmacokinetic or pharmacodynamics effects be detected.

Medical Condition Exacerbation: The most expected side effect of deprescribing is the return of the condition for which the medication was initially prescribed. A medication may be intentionally reduced or discontinued in the

absence of symptoms or signs to determine if the medication is still required to maintain control of a medical condition. In the Graves et al. study, 88% of all ADWEs were due to medical condition recurrence. Published data, however, does suggest that medication deprescribing for specific conditions (e.g., hypertension, osteoporosis, hyperlipidemia, angina) can be done without serious adverse effects. A strength of this trial is that we will be able to monitor for exacerbations of medical conditions in a post-acute care setting (mean length of stay = 26.9 days), where monitoring of vital signs and symptoms are done daily by licensed nurses. In addition, during the “SNF handover” process, all discontinued medications will be clearly delineated along with any expected signs or symptoms that may be expected to return. In addition, any necessary laboratory or diagnostic study follow-up will be recommended, as necessary. Medications can be restarted or increased at any time should condition signs or symptoms recur.

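### The planned safety hazard ratios include no randomized comparison of the early period in which the protocol places withdrawal reactions; fixed windows from randomization should be added.

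*Combined protocol and SAP*

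**What the plan says.** Safety Analyses specifies a Cox model for "the hazard of death (overall and separately within study phase"), and for recurrent events a frailty version: "The effect of the intervention on the hazard of each adverse event type (overall and separately within study phase"). On duration, "the maximum follow-up period for mortality (and other safety outcomes) is 90 days after SNF discharge". Timing is otherwise covered by counts and rates, overall and by phase, and by graphical checks of the Cox assumptions; no analysis is named for the case where those checks fail.

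Interventions and Duration identifies the hospital stay and the PAC stay as Phases 2 and 3. Data Analyses, in a paragraph whose title includes safety outcomes, limits analyses to randomized patients who complete Phase 2 by discharge to a partner facility, while also promising intent-to-treat and per-protocol analyses.

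The risk section reports, from one cited retrospective outpatient study, "All reactions occurred within 30 days of discontinuation". It also gives the PAC stay: "mean length of stay = 26.9 days". Interim analyses and Stopping Rules tells the DSMB to weigh the statistical evidence "as summarized by the relative hazard of safety endpoints and the corresponding 95% confidence interval", together with practical and clinical considerations.

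**The concern.** If deprescribing raises risk, the protocol's own evidence suggests that it does so soon after a drug is stopped. Thirty days is about a quarter of follow-up, so a single ratio over the whole period averages an early excess with a long stretch in which there may be none.

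The phase ratios look at shorter periods, but their boundaries are discharges that happen after randomization, differ between patients and could be shifted by the intervention. The PAC and post-PAC risk sets contain only patients who survived and stayed in the study to that point. The hospital phase does start at randomization, but it ends at a variable date and does not cover 30 days. A drug stopped late in PAC has much of its 30-day period in the next phase.

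The Phase 2 restriction, if applied to safety, would also drop in-hospital deaths and patients not discharged to a partner facility. At stake is whether the trial can make a clean comparative statement about early harm.

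**Working it through.** **Inputs from the documents**
- Enrollment: 144 × 4 = 576; with 1:1 allocation, 288 per arm. The plan's completer figure is reproduced: 576 × (1 − 0.275) = 417.6, against the stated 420. No event count or power is given for safety.
- Follow-up: 26.9 + 90 = 116.9 days before hospital time. Patients "expected to discharge from VUMC in less than 48 hours" are excluded, but no mean stay is given; I assume 0 to 10 hospital days after randomization. Total: 116.9 to 126.9 days. Thirty days is 30/116.9 = 26% to 30/126.9 = 24% of this.
- Event rate: the only one given is for participants "readmitted to VUMC directly from PAC (estimated 20"%).

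**Assumptions**
- Constant hazard λ = −ln(0.8)/26.9 = 0.0083 per day.
- True ratio of 1.5 or 2 in days 0-30 from randomization, and 1 afterwards.
- Frailty variance θ between 0 and 1.

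**Overall ratio** = (30 × HR + 87)/117.
- HR 1.5: (45 + 87)/117 = 1.13.
- HR 2: (60 + 87)/117 = 1.26.
- If the baseline hazard in days 0-30 is m times the later one, the ratio is (30m × HR + 87)/(30m + 87). For m = 2 and 3 this gives 1.20 and 1.25 (HR 1.5), or 1.41 and 1.51 (HR 2).

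**PAC-phase ratio** = 1 + f × (HR − 1), where f is the share of PAC person-days that falls before day 30.
- Fixed stay of 26.9 days and no hospital days: f = 1, so the ratio is 1.5 for HR 1.5.
- Exponential stay and 10 hospital days: f = 1 − exp(−20/26.9) = 0.52, giving 1.26.
- Less variable stay (gamma, shape 4) and no hospital days: f = 0.85, giving 1.42.

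**Power** (two-sided 0.05). Events per arm = 288 × λ × hazard-weighted days; SE of the log ratio = √(1/e0 + 1/e1 + 2θ/288). Ranges run from θ = 1 to θ = 0. The PAC row is the favorable case of a fixed stay and no hospital days.

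| Comparison | Events at HR 1.5 (control, intervention) | Power, HR 1.5 | Power, HR 2 |
|---|---|---|---|
| Overall, 117 days | 279.5, 315.4 | 18-31% | 51-81% |
| PAC phase, 26.9 days | 64.3, 96.4 | 61-71% | 98-99% |
| Days 0-30 | 71.7, 107.5 | 65-76% | 98.6-99.8% |

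For rarer events the order is the same at lower power. With 576 patients, HR 2 and an assumed control 30-day risk of 5%, power is 0.62 for days 0-30 against 0.28 overall; at 10% it is 0.89 against 0.51.

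**Simulation** (2,000,000 patients, frailty variance 1, mean hospital stay 7 days, PAC stay correlated with frailty, two assumed event rates). With a true early ratio of 2:
- overall 1.22-1.24
- hospital 1.95-1.98
- PAC 1.48-1.51
- after PAC 0.99-1.03
- days 0-30 1.90-1.98

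With no true effect but a 25% longer PAC stay on intervention, the PAC-phase ratio is 0.94 and the 0-30-day ratio 0.99-1.00.

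**Timing of stops.** The 30 days run from discontinuation, not randomization. Suppose a 2-fold excess runs over days 15-45: the 0-30-day ratio is (15 + 15 × 2)/30 = 1.5. Over days 28-58 it is (28 + 2 × 2)/30 = 1.07. A 0-60-day window gives (30 + 30 × 2)/60 = 1.5 in both cases.

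**The case against.** The strongest reply is that the plan already looks inside the early period. The PAC phase overlaps most of it, and under the favorable assumptions above its ratio keeps nearly all the power of a 0-30-day window (61-71% against 65-76%). Withdrawal events have their own blinded adjudication, and if they occur only early there are no late null events to dilute their ratio. The DSMB chair receives monthly listings by event type and group, and the board may request data and propose safety analyses. The bias in the phase ratio was small in the one null case simulated (0.94).

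Most of this stands. A reader might infer that an early excess would be reported as a ratio near 1 and that the DSMB would miss it. The documents do not support that: the phase ratios, the adjudicated endpoint and the monthly listings would each show part of a real excess, and the stopping section does not confine the board to an overall ratio.

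It is also fair that the 30-day figure comes from one outpatient study, that deprescribing can continue through PAC, and that the risk section names return of the treated condition as the most expected effect. The overall ratio therefore remains relevant, and a 0-30-day window alone would miss late stops. Nor would separate ratios for days 31-60 or after day 60 be cleaner than the phase ratios, since they too include only survivors.

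What does not fall away is that none of these safeguards supplies a comparison, over a fixed early period, of the groups as randomized. Adjudication classifies individual events, listings are descriptive, and the phase ratios depend on discharge dates.

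**Conclusion.** The gap is real and moderate. On the text alone, no planned safety ratio compares everyone randomized over a fixed early period. The overall ratio would show a 1.5-fold excess in days 0-30 as 1.13 and a 2-fold excess as 1.26, or about 1.20-1.25 and 1.41-1.51 if early baseline risk is two to three times the later risk. The PAC-phase ratio would show roughly 1.3 to 1.5 for a 1.5-fold excess, so the signal is weakened rather than hidden, but that ratio cannot be read as a randomized effect.

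The size rests on assumed early ratios, a constant hazard extrapolated from a PAC readmission figure, assumed frailty and hospital stay, and 288 per arm with no loss. The documents give no death rate (the 27.5% attrition mixes deaths with other losses), so no figure here applies to mortality. The textual point needs none of these assumptions.

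**What to change.** In Safety Analyses:
- Add supplementary comparisons over two cumulative windows from randomization, days 0-30 and days 0-60, for death and each adverse event type including adjudicated withdrawal events. The second window is needed because deprescribing continues in PAC.
- State that all randomized patients enter at day 0 whether or not they complete Phase 2, and that the Phase 2 restriction in Data Analyses does not apply to these comparisons.
- Label the phase-specific ratios, and any ratio for a window starting after day 0, as descriptive.

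In Interim analyses and Stopping Rules, list the two windows beside the overall ratio in the DSMB summary.

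The cost is SAP wording and one more table, largely from data already collected. The protocol withdraws patients who go home instead of to a partner facility or who move to hospice, so the number censored in each window should be shown by group. The downside is a few more safety intervals to interpret.
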